Beginning at the baseline visit (in person) and continuing daily throughout the intervention (online), participants will be asked to complete a child-adapted version of the validated Caffeine Withdrawal Symptoms Questionnaire (CWSQ). During the baseline visit, child participants will taste a small sample of each study beverage in pairs and will rate which beverage they like better and which beverage tastes sweeter using the enclosed beverage taste testing form. Child participants will be randomized into one of three study arms, where they will be instructed to replace their usual caffeinated SSBs with either: caffeinated SSB's provided by the study team, caffeine-free SSBs (caffeine-free Pepsi) or unsweetened sparkling water (LaCroix), compared to control (regular Pepsi consumption) for two weeks. All beverages will be provided by the study team, including drinks for the control group. After randomization, participants (child and parent together) will complete a daily online compliance questionnaire.

An outline of the schedule of study activities is below:

Time	Activity
Baseline Study Visit (Day 0) 1.5 hours	
 • Consent/assent • Height and weight • Complete in-person Caffeine Withdrawal Symptoms Questionnaire (CWSQ) with parent and child [this is called Daily Feelings Questionnaire in the Assent Form for kid-friendly language] • Dietary recall (parent and child)

	
 • Beverage taste testing (child) • Randomization and counseling regarding intervention (parent and child) • Provision of study beverages

Intervention (Days 1-14) Total of 1 hour per week
	
 • Parents receive three times weekly text message/email/phone reminders (based on participant preference) from study team • Parent and child together complete daily online CWSQ • Parent and child together complete daily online compliance survey • Child participant consumes assigned study beverages

Mid-intervention Visit Or Telephone Check-in (after first week of intervention)
 
~30-45 minutes
	
 • Complete in-person Caffeine Withdrawal Symptoms Questionnaire (CWSQ, parent and child together) • Dietary recall (parent and child together) • Provision of additional study beverages if needed • Participants and their parents encouraged to ask questions or express concerns

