
Follow-up visit (Day 15) 1.5-2 hours
	
 • Complete in-person Caffeine Withdrawal Symptoms Questionnaire (CWSQ, parent and child together) • Dietary recall (parent and child together) • Beverage taste testing (child participant) • Return empty study beverages • Qualitative interview (~20 minutes, parent and child together)

Details of all study procedures are described below:

Study Procedure	Description
Height and weight	Child participant's height and weight will be measured using a portable scale and stadiometer.
Caffeine Withdrawal Symptoms Questionnaire (CWSQ)	Parent and child participants will together complete a child-adapted version of the validated CWSQ ⁸ in person at baseline, and online daily throughout the intervention. [name] and/or a trained RA will assist with CWSQ completion at baseline and will counsel participants regarding filling out the online questionnaire.
24 hour dietary recalls	Participants will be asked (with the help of their parent) to report everything that they eat and drink over the past 24 hours. 24-hour recalls will be conducted at baseline (in person), after 1 week of the intervention (in person or via phone depending on participant preference), and at follow-up (in person).
Beverage taste testing	Prior to randomization, child participants will taste pairs each study beverage (10 mL) in randomized order and rate which beverage they like better and which beverage tastes sweeter using the taste enclosed taste testing form. Participants will rinse with water between each test. Taste testing will be completed in a private room and supervised by trained RAs. Child participants will also complete taste testing at follow-up.
Compliance questionnaires	Participants (child and their parent) will complete an online, 4-item questionnaire daily throughout the intervention to assess compliance (percentage of assigned beverages consumed, assessment of whether caffeinated SSB were consumed in violation of the study protocol, and if so, the brand and quantity consumed).
Randomization and Blinding	Following baseline assessments, child participants will be randomized using sex-stratified permuted block randomization into one of three arms: 1) caffeine-free SSBs (caffeine-free Pepsi) 2) unsweetened sparkling water (LaCroix) or 3) control (Pepsi).

	Assigned beverages will replace usual caffeinated SSB consumption, as assessed at enrollment.

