Compliance with beverage consumption will be assessed using beverage/compliance logs (completed by the parent and child together). We will operationalize compliance as the number of days in which participants consumed the study beverages, the total number of study beverages consumed during the intervention period, as well as any consumption of caffeinated SSB, juices etc. (in violation of the study protocol). Importantly, participants are being instructed simply to consume the study beverages in the same manner that they would normally consume their usual caffeinated sugar-sweetened beverages. They will not be assigned to consume a certain number of study beverages, but instead instructed to replace their usual beverages with the study drinks or water throughout the intervention period.

Liking of study drinks may affect compliance and we will therefore run exploratory multivariable linear regression models including taste ratings as a potential confounder, along other potential covariates such as sex, race/ethnicity, age, weight, and volume of habitual SSB consumption. While we recognize that we are not sufficiently powered for multivariable regression models including a large number of covariates, these data will be critical in informing sample size calculations for our subsequent R01 proposal. We will use an intention to treat (ITT) approach and will minimize loss to follow-up by maintaining close contact with participants. All analyses will be conducted using SAS 9.4.

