Sports Drinks (e.g. Gatorade, Powerade, etc.)												
Diet/Artificially Sweetened Sports Drinks (e.g. Powerade Zero, G2)												

IRB NUMBER: NCR191271
 IRB APPROVAL DATE: 06/07/2019

Beverage Taste Testing Form

Instructions for Pediatric Subjects. Show the cups to the subject and say: "We're going to play a game with things to taste. Here are two cups. You will taste what's inside the first cup, swish it around your mouth (BUT don't swallow) and I will tell you when to spit it out in the big cup. You will then rinse your mouth with water and then taste what's inside the second cup. I will tell you when to spit it out. Then I want you to POINT TO which one you like better - the first one or the second one. You will then rinse your mouth 2 times with water and we will do this again."

Notes:

- Be sure to underline which concentration is in position 1 for each pair.
- Use stopwatch to time solution in mouth for 5 seconds, and 1 minute between pairs
- Circle the

	Which one do you like better?				Which one is sweeter?				Notes
	A	B	C	D	A	B	C	D	
1.									
2.									
3.									
4.									
5.									
6.									

Qualitative Interview/Debrief Questions

- a) How difficult was it for your child to drink only the study drinks?
- b) Were other sodas/sugar-sweetened beverages available in the house during the intervention?
- c) Did your child drink these other beverages? How much do you think?
- d) How much oversight do you have over their beverage intake? Do you think they got other beverages elsewhere? Did they sneak soda/sugar-sweetened beverages?
- e) Did your consumption change at all as a result of participating in this study? How so?
- f) What was the hardest part of participating in this study?
- g) What was the best part of participating in this study?
- h) Anything else that you can tell us about your experience in this study?

Reminder Messages

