Liking of study drinks may affect compliance and we will therefore run exploratory multivariable linear regression models including taste ratings as a potential confounder, along other potential covariates such as sex, race/ethnicity, age, weight, and volume of habitual SSB consumption. While we recognize that we are not sufficiently powered for multivariable regression models including a large number of covariates, these data will be critical in informing sample size calculations for our subsequent R01 proposal. We will use an intention to treat (ITT) approach and will minimize loss to follow-up by maintaining close contact with participants. All analyses will be conducted using SAS 9.4.

Dietary intake will be collected through dietary recall interviews (completed by the parent and child together). This will allow us to assess adherence to the study beverages as replacements for habitual caffeinated SSBs and to determine if caffeinated SSB removal impacts dietary choices. While we acknowledge limitations inherent to self-report dietary assessment, dietary recalls are sufficient for capturing beverage consumption data and will enable us to determine whether participants change their diet to compensate for caffeine restriction.

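### The taste-test form records only relative preference within pairs, so it gives no absolute liking score for the planned regression, and no rule turns the choices into a covariate

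*Protocol*

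**What the plan says.** Protocol section D has each child taste the study drinks two at a time, before randomization and again at follow-up, and "rate which beverage they like better and which beverage tastes sweeter using the taste enclosed taste testing form". The randomization row of the procedures table names three drinks, one per arm: "1) caffeine-free SSBs (caffeine-free Pepsi) 2) unsweetened sparkling water (LaCroix) or 3) control (Pepsi").

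The form is in section Q (Beverage Taste Testing Form). Its script asks for a choice between two cups: "Then I want you to POINT TO which one you like better - the first one or the second one". The recording grid has one block for the better-liked drink and one for the sweeter drink. Each block has columns A to D, and the grid has six numbered rows and a notes column. A note to staff reads "Be sure to underline which concentration is in position 1 for each pair". There is no graded scale.

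The data analysis part of section D argues that liking of the drinks may influence compliance, and so plans "exploratory multivariable linear regression models including taste ratings as a potential confounder". The SAP repeats this, again "including taste ratings as a potential confounder". Both documents concede that they lack power for models with many covariates, but say that the data will inform the sample size of a follow-on grant application.

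**The concern.** The regression is meant to take account of how much a child likes the drink he or she was given. The form shows which of two drinks a child prefers, not whether the child likes either.

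The protocol's own worry is largely about absolute dislike. Section G notes that some children may not enjoy the drinks supplied. The limitations paragraph of section D says that children unused to seltzer may resist it. Aim 1 expects the lowest compliance in the sparkling-water arm. A child in that arm who ranks sparkling water last may still find it acceptable or may refuse it, and the form cannot tell these two children apart.

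Two further gaps matter. Neither document says how paired choices become a regression variable. The form also appears to have been laid out for a different set of products, which leaves staff to decide how to use it. Baseline liking that is not recorded cannot be recovered later, because the follow-up tasting comes after two weeks on the assigned drink.

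**Working it through.** The plan gives no figure to reproduce here. The check is a count of what the form can record, followed by a comparison of the passages.

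**Inputs.** Three study drinks (protocol section D, randomization row). A forced choice within each pair, columns A-D and six rows (section Q form). Tasting at baseline and follow-up (section D, procedures table).

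**1. Pairs and possible scores with three drinks.**
- Pairs: C(3,2) = 3.
- Choice patterns: 2^3 = 8. Two of these are circular; the other six are the 3! = 6 strict rankings.
- Pairs won by a given drink: 0 in 2 patterns, 1 in 4 patterns, 2 in 2 patterns.
- Each pair has one winner, so the wins over the three drinks always sum to 3.

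Because the total is fixed, the data carry no information on a child's overall level of liking. Take two children with the same order of preference, one who enjoys all three drinks and one who dislikes all three. Both produce wins of 2, 1 and 0, and no scoring rule separates them.

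**2. The grid.**
- Four products: C(4,2) = 6 pairs, which matches six rows and columns A-D. A drink could then win 0 to 3 pairs, and the wins would sum to 6.
- Three products tasted in both orders: 3 x 2 = 6 rows. This also fits the rows, but column D has no product. The wins again have a fixed sum (6), so the data remain relative.

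**3. Script against grid and procedures.** Section D requires children to "rate which beverage they like better and which beverage tastes sweeter". The grid prints both questions, but the spoken script asks only about liking. The staff note refers to a concentration, although the drinks are commercial products with no stated concentrations. The notes appear to break off in mid-sentence; that may be a PDF reading loss, and nothing here rests on it.

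**4. Other sources of a liking score.** The daily compliance questionnaire asks what was drunk and how much. The debrief asks how hard it was to keep to the study drinks. Neither contains a rating of liking for a drink.

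**5. Definition of the covariate.** Neither document says which choices are used, whether the variable refers to the assigned drink, or whether the baseline or the follow-up tasting supplies it.

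**The case against.** The strongest reply is that the ratings in the analysis plan simply are the paired results. Section D uses the verb in that sense: "child participants will taste a small sample of each study beverage in pairs and will rate which beverage they like better". Section G lists the tasting under a heading that calls it ratings. This part stands. A reader might infer that no taste rating is ever collected, but relative preference is collected twice, and a pairs-won score or an indicator that the assigned drink was preferred could enter the model. Relative preference is also relevant, because compliance here means replacing the usual drink. What the reply does not supply is absolute liking or a derivation rule.

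A reader might also infer that a pairs-won score would merely re-code the arm. The documents do not support this. They give no data on how children split between the two colas or between cola and sparkling water, so any figure for overlap with arm depends on assumed preferences. A 0-4 liking score may be just as collinear with arm if children like sparkling water less. Collinearity is therefore no argument for one measure over the other.

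The layout points are minor and do not prevent data collection. Column D may be left unused. It may also hold a second sparkling-water flavor: section G mentions flavored water, but not how many flavors, and does not link it to the form.

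Finally, the regression is exploratory and acknowledged to be underpowered. That stands and limits the weight of this point.

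**Conclusion.** The form yields relative preference only: with three drinks, a three-level score per drink with a fixed total of 3 per child. It cannot show whether a child likes the assigned drink in absolute terms, and no rule turns its choices into the planned covariate. It also does not fit the trial in its columns, its reference to concentration and its script. These findings follow from the documents by counting and need no assumption about children's preferences.

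The consequence is small. It reaches the exploratory regression and the planning of the follow-on study. A reader might take it to undermine the main comparisons, but the one-way ANOVAs of compliance (primary) and withdrawal symptoms (secondary) use no taste data. Whether liking is rightly called a confounder in a randomized comparison is a separate question. This is a cheap improvement, worth making because the baseline measurement cannot be obtained afterwards.

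**What to change.** Before the first baseline visit:

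- Revise the form for the three study drinks (columns A-C, three pairs) and remove the reference to concentration. If both tasting orders or a second flavor are intended, say so on the form.
- Add a short liking score, for example five faces scored 0-4, after the 10 mL sample. One score per drink, at its first tasting, is enough, giving three scores per visit.
- Keep both paired questions that section D promises, and add the sweetness question to the spoken script. Dropping the paired liking question would remove a planned measure and its comparison between baseline and follow-up.
- In the protocol's data analysis text and in the SAP, define the covariate as the pre-randomization liking score of the assigned drink. Name the baseline paired preference for the assigned drink against regular Pepsi as a secondary descriptor. It exists only in the two replacement arms (2 x 20 = 40 of the 60 planned children), because in the control arm the assigned drink is regular Pepsi.

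The cost is an estimated 1-2 minutes per visit, an IRB form revision, and short wording changes in the protocol and SAP. Arms, sample size and the main analyses are unchanged. If the score cannot be added, the minimum is to pre-specify a baseline score from the paired choices and state that it measures relative preference only.

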The following reminders will be sent to parents during the intervention:

“Hi ___[insert parent name]__. This is a friendly reminder to please complete the study questionnaires.”

“Hi ___[insert parent name]__. This is a friendly reminder to please remind ___[insert child name]_ to drink only the study drinks provided until ___[insert date of follow-up visit]__.”

DOES YOUR CHILD LIKE SODA OR SWEET TEA?

RECRUITING CHILDREN 8-11 YEARS OLD

Please consider participating in our study!

\$175 Compensation

- **What does participating involve?**
The study involves asking your child to drink sugar-free and/or caffeine free soft drinks for two weeks. We will ask your child to complete daily questionnaires and participate in telephone interviews about their diet for three weeks.
- **Is my child eligible?**
Your child may be eligible if they are 8-11 years old and drink at least 12 ounces of sugar sweetened caffeinated beverages per day.

**For more information, contact The George Washington University
study team at: [contact].**

¿LES GUSTAN A SUS HIJOS SODA O TÉ DULCE?

Reclutando a Niños 8-11 años

Por favor, considere participar en nuestro estudio.

\$175 de Reembolso

- **¿Que implica participar?**
El estudio implica pedir a su hijo tomar bebidas sin azúcar y/o cafeína por dos semanas. Pediremos que su hijo complete cuestionarios diarios y participe en entrevistas telefónicas sobre su dieta por tres semanas.
- **¿Es elegible mi hijo?**
Su hijo pueda ser elegible si tiene 8-11 años y si tome por lo menos 12 onzas de bebidas azucaradas con cafeína cada día

**Para más información, por favor, contactor el equipo de estudio del
George Washington University a: [contact]**

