Official Title: Investigating Withdrawal Symptoms as Barriers to Reducing Sugar-sweetened Beverage Consumption among Children

NCT #: Not yet assigned

Date: July 15th, 2019

Statistical Design and Power

The primary purpose is to evaluate primary the feasibility of the intervention and therefore, formal sample size calculations for clinical outcomes were not performed. We will enroll a total of 60 participants (n=20 per group).

This study includes an intervention to remove caffeinated SSBs and to explore whether caffeinated SSB removal induces withdrawal symptoms in 8-11 year old (3rd-5th grade) children. Child participants in the clinical pilot study will be randomly assigned to replace their usual caffeinated SSB consumption with either caffeinated SSBs provided by the study team, caffeine-free SSBs or unsweetened sparkling water (also provided by the study team) for two weeks.

Caffeine withdrawal scores will be collected using caffeine withdrawal symptom questionnaires (CWSQ, completed by the child and parent together). Peak withdrawal symptoms will be operationalized as CWSQ scores reported within the initial 72 hours of the intervention, between the three groups. Univariate analyses and one-way ANOVA will be used to assess group differences in our primary (measures of compliance with beverage intervention) and secondary (withdrawal symptoms) study outcomes.

Compliance with beverage consumption will be assessed using beverage/compliance logs (completed by the parent and child together). We will operationalize compliance as the number of days in which participants consumed the study beverages, the total number of study beverages consumed during the intervention period, as well as any consumption of caffeinated SSB, juices etc. (in violation of the study protocol). Importantly, participants are being instructed simply to consume the study beverages in the same manner that they would normally consume their usual caffeinated sugar-sweetened beverages. They will not be assigned to consume a certain number of study beverages, simply to replace their usual beverages with the study drinks and to consume only the study drinks and water throughout the intervention period.

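### Both recruitment flyers describe only removal of sugar and/or caffeine, omit chance assignment and the regular-cola control arm (20 of 60 children), and state three weeks where the schedule ends on Day 15

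*Protocol*

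**What the plan says.** **The flyers (Protocol section Q, Appendix).** The English flyer describes participation as follows: "The study involves asking your child to drink sugar-free and/or caffeine free soft drinks for two weeks". It adds that the child will "complete daily questionnaires and participate in telephone interviews about their diet for three weeks". The Spanish flyer says "El estudio implica pedir a su hijo tomar bebidas sin azúcar y/o cafeína por dos semanas" and "participe en entrevistas telefónicas sobre su dieta por tres semanas". Neither mentions randomization, a control group or regular soda, and neither mentions an in-person visit.

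**The design (Protocol section D).** The Randomization and Blinding entry of the procedures table lists the arms: "1) caffeine-free SSBs (caffeine-free Pepsi) 2) unsweetened sparkling water (LaCroix) or 3) control (Pepsi". The design text confirms that controls also receive study drinks: "All beverages will be provided by the study team, including drinks for the control group". The SAP, under Statistical Design and Power, states: "We will enroll a total of 60 participants (n=20 per group".

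**The schedule (Protocol section D).** There is a baseline visit on Day 0 (1.5 hours), an intervention on Days 1 to 14 with daily online questionnaires, a check after the first week, and a follow-up visit on Day 15 (1.5 to 2 hours). The dietary recall entry sets three recalls. The baseline and follow-up recalls are in person; the week-1 recall is in person or by telephone.

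**The concern.** The flyers advertise a study in which every child gives up sugar, caffeine or both. One arm gives up neither. The stated length and mode of contact also differ from the schedule.

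Two consequences are plausible.

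- **Who responds.** Aim 1 is the feasibility of removing caffeinated sugar-sweetened beverages, and compliance is the primary outcome. A flyer that mentions only removal may draw more families who already want to cut down. Feasibility would then be estimated in a favourable part of the habitual-consumer population, and that estimate is meant to inform a larger intervention.
- **How controls behave.** Children are given no set number of study drinks and may take water instead (section D, Data analysis and Beverage distribution). A control family that came in order to cut soda could switch to water without breaking any rule. That would lower the count of study drinks consumed and possibly the number of days on which they are consumed, both named compliance measures. It would also lower control caffeine intake and so narrow the contrast for withdrawal symptoms in Aim 2.

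Apart from any bias, recruitment text for a study in children should describe the study that will be run.

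**Working it through.** **1. Share of children for whom the drink description is untrue.**
Inputs: three arms (Protocol section D); 20 per group, 60 in total (SAP).
- The plan's total is reproduced: 3 × 20 = 60.
- Caffeine-free Pepsi is caffeine-free, and sparkling water is free of both sugar and caffeine, so the sentence holds for those arms.
- Regular Pepsi is neither, so the sentence fails for 20/60 = 33.3%.

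**2. Duration.**
Inputs: three weeks (flyers); Day 0 to Day 15 (schedule).
- Flyers: 3 × 7 = 21 days.
- Schedule: 15 − 0 = 15 elapsed days, or 16 calendar days counting both ends.
- Overstatement: 21 − 15 = 6 days (6/15 = 40%), or 21 − 16 = 5 days (5/16 = 31%).
- If the three weeks are read as covering the daily questionnaires too, the comparison is 21 days against 14 (Days 1 to 14).

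**3. Mode of diet interviews.**
- Flyers: telephone interviews.
- Schedule: three recalls, two fixed as in person and one optional. At most 1 of 3 is by telephone.

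**4. Do the two flyers agree?** They agree on sugar and/or caffeine, on two weeks of drinks and on three weeks of interviews. They differ in one respect. The English text refers to soft drinks, which a reader could take to mean diet soda; the Spanish text refers only to drinks. That reading therefore applies to the English flyer alone, and even there it is only one possible reading.

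**5. Where each possible effect would act.**
- Selection by the flyer happens before randomization. It affects all three arms alike in expectation, so it bears on generalizability and does not by itself bias the comparison between arms.
- A reaction to the assigned drink happens after randomization and could differ by arm. It requires families to know their arm. The daily compliance questionnaire in the Appendix inserts the specific assigned drink, so they can.

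**6. Can either effect be sized?** No. The documents give no share of families recruited by flyer, no measure of motivation and no expected control-arm intake. The demographic questionnaire has no item on recruitment source or wish to cut down, so the planned data would not show the reason for a lower control intake.

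**The case against.** The strongest case on the other side is that this is a paperwork correction with no shown effect on the results.

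- **The flyers do not preach quitting.** The headline asks whether the child likes soda or sweet tea, and $175 is advertised. That may draw soda-likers or families interested in the payment just as well. This stands: selection is possible, not shown.
- **Flyers are one route among several.** Sections D and F describe on-site recruitment by staff, community organizations and word of mouth. This stands and would dilute any effect.
- **Families are informed before randomization.** Section F has a verbal explanation of purposes and procedures, and signed consent and assent before any procedure. Children also taste each drink before assignment. The forms are not in the text reviewed, so whether they disclose the control arm cannot be checked. This weakens the control-arm argument. It cannot change who responded to a flyer.
- **Blinding may help.** The limitations paragraph in section D mentions an opaque wrapper. It concedes that this may be insufficient, and the compliance form names the drink, so little reassurance follows.
- **A correct flyer would also select.** Families willing to accept possible removal select themselves in any case. This stands: the fix removes an avoidable distortion, not all selection.
- **Low control intake would be seen.** Daily forms, recalls and returned containers record it. That is true of the amount, but not of the reason.

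A reader might infer that the flyers do select families who want to quit and set controls up for disappointment, or that control intake falls by some definite percentage. The documents support neither. They contain no evidence on motives or on families' reactions to assignment, and nothing from which to derive such a percentage.

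**Conclusion.** The discrepancy is certain, and its effect on the results is uncertain. The flyers are wrong about the drink for 20 of 60 children (33%), assuming the planned equal groups are met. They overstate the duration by 5 to 6 days and present as telephone interviews a set of recalls of which at least two of three are in person. They omit chance assignment altogether.

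Over-recruitment of motivated families is plausible and would limit the generalizability of the feasibility estimate in every arm. Reduced control-arm intake of study drinks is also plausible, because water may be substituted freely and the assigned drink is named to families; what families learn at consent may lessen it. Neither effect is demonstrated or quantified. The duration and mode errors misstate burden, and no bias is argued from them.

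The arms, endpoints and analysis do not need to change. The flyers should be corrected because they are inaccurate as written and the correction is cheap.

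**What to change.** Revise both flyers together.

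- **Drink and assignment.** Replace the description with one that is true of all arms, for example: *Instead of their usual soda, your child will be assigned by chance to one of three drinks for two weeks: regular cola, caffeine-free cola or unsweetened sparkling water.* Use equivalent wording in Spanish.
- **Schedule.** Replace the three-week statement with the Day 0 to Day 15 schedule in section D: two weeks of daily online questionnaires, in-person visits at the start and end, and a week-1 check in person or by telephone. State that only the week-1 recall may be by telephone.
- **Optional.** Add baseline items on recruitment source and on the family's wish to cut down, so that both possible effects can be described in the pilot report.

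The cost is a two-language edit and a minor ethics-board modification. Interest may be somewhat slower from families who want only a removal arm. The optional items would add slightly to the baseline questionnaire.
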